5.5.1.2. Wrist Device Data Processing

Wrist device, including accelerometer data and PPG signals, will be uploaded by the subject at home.

Procedures for data analysis based on the data collected via the wrist device are described in Section 6.1.

5.5.2. Adjudication of ECG Data

5.5.2.1. ECG Patch

IRNF

ECG Patch Diagnosis (Primary Endpoint)

ECG patch data will be reviewed and adjudicated by the [REDACTED] Each ECG patch will be reviewed by a cardiac technician. The cardiac technician will review each ECG recording in its entirety [REDACTED]

[REDACTED] The cardiac technician will be instructed to review ECG patches independently and separately of each other and not to confer about diagnoses. All cardiac technicians will be blinded to subject cohort and IRNF notifications. [REDACTED]

[REDACTED] After the cardiac technician has completed their assessment of an ECG patch, the following procedure will be followed by US Board-Certified Cardiologists:

a) Each of the cardiac technician's ECG patch assessments will be reviewed by a Cardiologist who did not perform the initial assessment. ("Over-reader"). At no time may an over-reader who performed the initial assessment of the ECG patch, over-read their own assessment.

b [REDACTED]

c) If the over-reader determines the cardiac technician's assessments are consistent, they will approve the results and electronically sign the case without changes.

d) If the over-reader determines the cardiac technician's assessments require amendment, the over-reader will make the required changes and approve the results and electronically sign the case. All changes will be automatically tracked in a 21CFR11 compliant audit trail.

e) After the over-reader has completed their over-read, the results will be quality controlled [REDACTED]

ECG Strip Diagnosis (Secondary Endpoints)

ECG strips will be identified from the ECG patch for the period of time corresponding to each tachogram that was selected for analysis.

Il adjudicators will be blinded to cohort and

IRNF notifications.

AFBF

ECG AF Burden Measurement (Primary Endpoint)

ECG patch data will be reviewed and adjudicated by the [REDACTED] Each ECG patch will be reviewed by a cardiac technician. The cardiac technician will review each ECG recording in its entirety [REDACTED]

The cardiac technician will be instructed to review ECG patches independently and separately of each other and not to confer about diagnoses. All cardiac technicians will be blinded to cohort and IRNF notifications. After the cardiac technician has completed their assessment of an ECG patch, the following procedure will be followed by US Board-Certified Cardiologists:

a) Each of the cardiac technician's ECG patch assessments will be reviewed by a Cardiologist who did not perform the initial assessment. ("Over-reader"). At no time may an over-reader who performed the initial assessment of the ECG patch, over-read their own assessment.

c) If the over-reader determines the cardiac technician's assessments are consistent, they will approve the results and electronically sign the case without changes.

d) If the over-reader determines the cardiac technician's assessments require amendment, the over-reader will make the required changes and approve the results and electronically sign the case. All changes will be automatically tracked in a 21CFR11 compliant audit trail.

ECG Strip Diagnosis (Secondary Endpoint)

ECG strips will be identified from the ECG patch for the period of time corresponding to each tachogram that was selected for analysis.

Strips will be reviewed by 2 independent US

Board Certified Cardiologist adjudicators for a strip diagnosis (Section 5.5.2.1.1). If there are any differences in adjudication decisions, the strip in question will be sent to a third adjudicator for final decision. Adjudicators will be instructed to review ECGs independently and separately of each other and not to confer about diagnoses. All adjudicators will be blinded to cohort and AFBF information.

5.5.2.1.1. Rhythm Diagnoses

The diagnosis of the rhythm will fall into one of five categories:

1. Sinus Rhythm
2. Atrial Fibrillation (AF)
3. Atrial Flutter (AFL)
4. Other irregular rhythms (examples include sinus rhythm with frequent PACs, sinus rhythm with frequent PVCs, SVT, VT/VF)
5. Unreadable as defined that a diagnosis cannot be made as the strip is not adequate for reading

The diagnosis will be made via the following logic flow (in sequential order):

1. If the ECG strip contains at least 10 seconds of continuous atrial fibrillation, then it will be classified as “Atrial fibrillation.” Any atrial fibrillation with PACs or PVCs will be classified as “Atrial fibrillation”, with the note of PACs or PVCs be added to the comments section.
2. Otherwise, if 6 or more of the sub-strips cannot be interpreted (e.g. due to noise or artifacts), then the strip will be classified as “Unreadable.”
3. Otherwise, if the ECG strip contains a non-AF arrhythmia, then it will be classified as “Other arrhythmia”. This includes:
 - Supraventricular Tachycardia (includes atrial tachycardia, AVNRT, AVRT)
 - Sinus rhythm with PACs
 - Sinus rhythm with PVCs
 - Sinus rhythm with junctional beats
 - Sinus arrhythmia
 - Ventricular tachycardia (sustained or nonsustained)
 - Heart Block (includes 2nd or 3rd degree HB)
4. Otherwise, the ECG will be classified as “Sinus rhythm”

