6.2. Statistical Methodology

For all of the IRNF statistical analyses, atrial fibrillation (AF) and atrial flutter (AFL) will be treated as a single category of "AF". For all of the AFBF statistical analyses, atrial fibrillation (AF) will be considered its own unique category (i.e., atrial flutter will not be included as part of the detection of AF episodes).

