6.2.3. Secondary Endpoint Analyses

IRNF

The notification-level PPV of AF by ambulatory ECG at the time of any tachogram comprising the notification will be estimated for both the test and predicate device algorithms. The notification-level PPV is defined as the proportion of notifications where at least one of the ECG strip results associated with the spot tachograms that comprise the notification exhibits AF of at least 10 seconds per the ECG strip diagnosis definition presented in Section 5.5.2.1.

Notification-Level PPV = (# of notifications with an adjudicated ECG strip diagnosis of AF of at least 10 seconds for any tachogram comprising the notification) / (# of alert notifications)

For subjects who exhibit a high level ($\geq 95\%$) AF burden, it is expected that a large (100 to 200) number of notifications will be generated in total for both the IRN 1.0 and 2.0 algorithms resulting in $>1,000$ tachograms per subject in Cohort 4. For these subjects who are permanently in AF, a least burdensome approach will be followed where for all notifications generated from subjects in Cohorts 1 and 3 and randomly selected notifications from subjects in Cohort 4 will be included in this analysis. A corresponding adjudicated ECG strip diagnosis will be determined for all tachograms comprising these notifications.

Because the set of notifications may differ between the test and predicate device algorithms and because multiple notifications may be associated with some subjects, a bootstrap approach will be implemented to obtain 95% two-sided confidence intervals separately for each algorithm's notification-level PPV. The bootstrap sampling will randomly select subjects who have analyzable data with replacement rather than individual data points to account for any correlation structure that might exist within subjects so that confidence limits are corrected for within-subject correlation.

Two tachogram-level analysis results

associated with the secondary endpoints

of tachogram performance will be reported separately for each device algorithm using tachograms generated by subjects in Cohorts 1, 3, and 4. Separate contingency tables cross-classifying the adjudicated cardiologist diagnoses from ECG strips with the binary classification of tachogram results for test and predicate devices will be presented as outlined in [Table 7](#) below.

Table 7: Cross-Classification Table of Tachogram Results and Adjudicated Cardiologist Diagnoses from ECG Strips

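### The ECG strip classification flow has no step that outputs Atrial Flutter, although the category list, the IRNF pooling rule and the IRNF tachogram formulas all need that label

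*Combined protocol and SAP*

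**What the plan says.** Section 5.5.2.1.1 opens with "The diagnosis of the rhythm will fall into one of five categories"; the third of the five is Atrial Flutter (AFL). It then sets out four steps, to be applied in order:

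1. At least 10 seconds of continuous fibrillation gives Atrial fibrillation.
2. Otherwise, six or more uninterpretable sub-strips give Unreadable.
3. "Otherwise, if the ECG strip contains a non-AF arrhythmia, then it will be classified as" Other arrhythmia. The examples include SVT, ectopy, VT and heart block; flutter is not named.
4. Anything left is Sinus rhythm.

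The analysis sections treat AFL as a label of its own. Section 6.2 states: "For all of the IRNF statistical analyses, atrial fibrillation (AF) and atrial flutter (AFL) will be treated as a single category of" AF. For AFBF the same section keeps flutter out of AF. Table 7 in Section 6.2.3 has an Atrial Flutter column (n13, n23, nAFL), separate from Other Irregular Rhythm (n14, n24, nOA). Notification-level PPV counts a notification as correct when at least one of its strips "exhibits AF of at least 10 seconds per the ECG strip diagnosis definition presented in Section 5.5.2.1".

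**The concern.** The list promises a label that the assignment rule cannot deliver. If readers follow the steps, flutter joins Other arrhythmia and there are no AFL strips to pool with AF. Flutter tachograms called irregular then count as IRNF false positives and leave the PPV numerator. All flutter, flagged or missed, leaves the sensitivity calculation. A notification supported only by flutter strips counts against notification-level PPV. Each of these runs against Section 6.2. If readers follow the list instead, they have no minimum duration for flutter and no order relative to Unreadable, and two independent readers could resolve the conflict differently.

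**Working it through.** **Which labels the flow can reach.** It rests on three yes/no conditions: at least 10 seconds of continuous AF, at least six uninterpretable sub-strips, and a non-AF arrhythmia present. Of the eight combinations, four give Atrial fibrillation, two Unreadable, one Other arrhythmia and one Sinus rhythm. None gives Atrial Flutter. A readable pure flutter strip (no, no, yes) gives Other arrhythmia.

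**Effect on the Section 6.2.3 formulas.** Moving flutter from the AFL column to Other puts n13 into n14 and n23 into n24. With n14 and nOA denoting the counts before the move:

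- IRNF sensitivity: (n12+n13)/(nAF+nAFL) becomes n12/nAF. It reads too high if flutter is flagged less often than AF, and too low if more often.
- IRNF FPR: (n11+n14)/(nSR+nOA) becomes (n11+n14+n13)/(nSR+nOA+nAFL). It rises if flutter is flagged more often than the base FPR, and falls if less often.
- IRNF PPV: (n12+n13)/(nTI−n15) becomes n12/(nTI−n15). The denominator is unchanged, so PPV falls or stays the same.
- IRNF specificity n21/nSR and NPV n21/(nTN−n25): no flutter cell enters, and the totals do not change.
- AFBF metrics: sensitivity n12/nAF and PPV n12/(nTI−n15) contain no term that changes. Specificity and NPV use only the sums n23+n24 and nAFL+nOA.
- Section 6.2.5: Pr(Irregular | Other) becomes (n14+n13)/(nOA+nAFL), and the other probabilities involving Other Irregular Rhythm change likewise. The notification PPV that combines AF with other arrhythmias is unaffected.

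**Illustration; every input is assumed, because the documents give none.** Take 3,000 AF strips with 2,850 called irregular (95%), 9,000 SR and 1,000 Other strips each with a base FPR of 0.4% (n11 = 36, n14 = 4), no unreadable strips, and 150 flutter strips (5% of the AF count). The first figure is with flutter coded AFL, the second with flutter coded Other.

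| Flutter flagged | n13 | FPR | PPV | Sensitivity |
|---|---|---|---|---|
| 0% | 0 | 40/10,000 = 0.40%; 40/10,150 = 0.39% | 2,850/2,890 = 98.6%; same | 2,850/3,150 = 90.5%; 95.0% |
| 30% | 45 | 0.40%; 85/10,150 = 0.84% | 2,895/2,935 = 98.6%; 2,850/2,935 = 97.1% | 2,895/3,150 = 91.9%; 95.0% |
| 70% | 105 | 0.40%; 145/10,150 = 1.43% | 2,955/2,995 = 98.7%; 2,850/2,995 = 95.2% | 2,955/3,150 = 93.8%; 95.0% |
| 100% | 150 | 0.40%; 190/10,150 = 1.87% | 3,000/3,040 = 98.7%; 2,850/3,040 = 93.8% | 3,000/3,150 = 95.2%; 95.0% |

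In the 70% row, Pr(Irregular | Other) goes from 4/1,000 = 0.4% to 109/1,150 = 9.5%.

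With a base FPR of 5% (n11 = 450, n14 = 50), 150 flutter strips and 70% flagged, FPR goes from 5% to 605/10,150 = 5.96%, and PPV from 2,955/3,455 = 85.5% to 2,850/3,455 = 82.5%. With 30 flutter strips and 30% flagged (n13 = 9), FPR is 509/10,030 = 5.07%, and PPV goes from 2,859/3,359 = 85.1% to 2,850/3,359 = 84.8%.

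**Notification-level PPV (assumed counts).** If 194 of 200 notifications have an AF or AFL strip, PPV is 97%. If 2 of them rest on flutter alone it becomes 192/200 = 96%; if 10, 184/200 = 92%.

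**Cohort 2.** If the Section 6.2.3 FPR formula applies, each algorithm's FPR with flutter coded Other is (b + fq)/(1 + f), where b is the base FPR, f the ratio of flutter to SR-plus-Other strips, and q the flutter flag rate. With b = 0.4% for both algorithms:

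- f = 1% v 0.5%, q = 50% for both: 0.891% − 0.647% = 0.24 points.
- f = 1% for both, q = 50% v 40%: 0.891% − 0.792% = 0.10 points.
- f = 1% v 0.5%, q = 25.3% v 50%: 0.647% − 0.647% = 0.
- q = b for both: 0, whatever the shares.

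Differences between the algorithms can therefore cancel.

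**The case against.** The strongest reply is that board-certified cardiologists, told there are five diagnoses, will label flutter as flutter. The rest of the plan treats AFL as separate, and step 3's examples omit it. A reader might infer from the flow that n13 = n23 = nAFL = 0 is certain; the documents do not support that, since it follows only if the steps override the list. The omission itself stands. Reading the pooled AF of Section 6.2 into step 1 would label flutter as fibrillation, and AFBF could not separate it. Reading non-AF in step 3 as excluding flutter would drop a pure flutter strip through to Sinus rhythm. Neither reading outputs AFL.

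The second reply is that the IRNF link is incomplete. The IRNF strip paragraph in Section 5.5.2.1 survives only in part (a fragment saying "adjudicators will be blinded to cohort and" the notifications), and the visible pointer to Section 5.5.2.1.1 is in the AFBF paragraph. A flutter rule could sit in the lost text, or in the detail that the protocol defers to the SAP. This limit is real. Against it, Section 6.2.3 ties the IRNF strip diagnosis to Section 5.5.2.1, which contains the flow, and steps 1 to 4 are numbered without a gap and show no redaction.

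Third, a reader might infer that the Cohort 2 non-inferiority test is compromised. That is not shown. Flutter would have to occur there, and the algorithms' flutter shares or flag rates would have to differ without cancelling. The formula would also have to apply, yet Section 6.2.3 introduces the results "of tachogram performance will be reported separately for each device algorithm using tachograms generated by subjects in Cohorts 1, 3, and 4", and the Cohort 2 hypothesis in Section 2.2 is partly redacted, with no visible margin.

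**Conclusion.** The point holds as an internal inconsistency in the adjudication rule. The five-item list includes AFL; the flow that makes the diagnosis has no AFL output and, read literally, sends flutter to Other arrhythmia, against Section 6.2 and Table 7. It bears on secondary and additional IRNF estimates. The subject-level IRNF primary analysis uses the whole-patch report rather than the strip flow (Section 6.2.2), and nothing visible links the AFBF primary endpoint to it.

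The size is unknown, and the table above is illustration only. One might infer that the flow always makes IRNF look worse; that holds for PPV, if it moves at all, but not for sensitivity, which can move either way, nor for FPR, which falls slightly if flutter is flagged less often than the base rate. The conclusion assumes that no flutter rule exists in the text that cannot be seen.

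**What to change.** Before strips are read, add an explicit Atrial flutter step ahead of step 3, with a stated minimum duration (for example 10 seconds, to match step 1 and the notification-level PPV definition). State its order relative to Unreadable: placed before that step, it brings some strips that would otherwise be unreadable into the IRNF and AFBF denominators. Limit step 3 to arrhythmias not already classified as AF or AFL. If a flutter rule already exists in text not visible here, move it into the flow. The cost is a short edit to the adjudication rule, with no extra readers or data; left until after reading, it could mean re-adjudicating strips labelled Other arrhythmia.

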Tachogram Result	Adjudicated Cardiologist Diagnosis					Total
	SR	AF	Atrial Flutter	Other Irregular Rhythm	Uninterpretable	
Irregular	n11	n12	n13	n14	n15	nTI
Not AF	n21	n22	n23	n24	n25	nTN
Total	nSR	nAF	nAFL	nOA	nU	N

Abbreviations: SR = sinus rhythm; AF=atrial fibrillation; AFL=atrial flutter

Tachogram performance for the test and predicate devices will be estimated separately as outlined below because the set of tachograms will differ by device. Two-sided 95% bootstrap confidence intervals will be constructed for each performance metric by randomly selecting subjects who have analyzable data with replacement to account for any within subject correlation of multiple tachograms associated with each subject.

Tachogram Sensitivity = $(n12+n13)/(nAF+nAFL)$

Tachogram Specificity = $n21/nSR$

Tachogram False Positive Rate = $(n11+n14)/(nSR+nOA)$

Tachogram PPV = $(n12+n13)/(nTI-n15)$

Tachogram NPV = $n21/(nTN-n25)$

The ECG strips corresponding to all tachograms which comprise each notification for subjects in Cohorts 1, 3 and 4 from the test and predicate device algorithms will be adjudicated and included in the analysis of this secondary endpoint.

AFBF

A tachogram-level analysis associated with the secondary endpoint of tachogram performance for the AFBF will be reported by cross-classifying the binary classification of tachogram results with the adjudicated cardiologist classifications from ECG strips where the SR and Other Abnormal Rhythm adjudications are combined into a single category. [REDACTED]

Using the notation of [Table 7](#), tachogram performance will be estimated as outlined below from the randomly selected tachograms for all subjects in Cohorts 3 and 4. Two-sided 95% bootstrap confidence intervals will be constructed for each performance metric to account for potential within subject correlation of the multiple tachograms associated with each subject.

- Tachogram Sensitivity = $n12/nAF$
- Tachogram Specificity = $(n21+n23+n24)/(nSR+nAFL+nOA)$
- Tachogram PPV = $n12/(nTI-n15)$
- Tachogram NPV = $(n21+n23+n24)/(nTN-n25)$

Although the set of tachograms for the AFBF device algorithm will differ from the set of tachograms generated from the test IRNF device algorithm, [REDACTED]

[REDACTED] The same tachogram performance analysis of the AFBF device algorithm will be performed as specified above.

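### The strip-reading steps label a readable strip whose only abnormality is AF under 10 seconds as Sinus rhythm, which distorts IRNF tachogram specificity, NPV and the Other-rhythm outputs

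*Combined protocol and SAP*

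**What the plan says.** Section 5.5.2.1.1 (Rhythm Diagnoses) lists five rhythm categories and then four steps to be applied in order:

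1. "If the ECG strip contains at least 10 seconds of continuous atrial fibrillation, then it will be classified as" atrial fibrillation. A second sentence adds: "Any atrial fibrillation with PACs or PVCs will be classified as" atrial fibrillation, and repeats no minimum duration.
2. "Otherwise, if 6 or more of the sub-strips cannot be interpreted", the strip is Unreadable.
3. "Otherwise, if the ECG strip contains a non-AF arrhythmia, then it will be classified as" Other arrhythmia. The list under this step includes sinus rhythm with PACs, sinus rhythm with PVCs and sinus arrhythmia, none with a minimum duration or frequency.
4. "Otherwise, the ECG will be classified as" sinus rhythm.

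Section 6.2.3 turns these labels into IRNF tachogram metrics through Table 7. Specificity is n21/nSR. The false positive rate (FPR) is (n11+n14)/(nSR+nOA). PPV is (n12+n13)/(nTI−n15), and NPV is n21/(nTN−n25). AFBF tachogram specificity pools sinus rhythm, flutter and other rhythms. Section 6.2.5 adds device results conditional on Other Irregular Rhythm, tables by Other sub-category, and a notification-level PPV for AF and other arrhythmias combined.

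**The concern.** AF is not a non-AF arrhythmia, so no step covers AF shorter than 10 seconds. A readable strip with one such run, or several separate ones, and no other listed arrhythmia drops to the default and is recorded as Sinus rhythm. The plan is then stricter about a strip with PACs, which may not be called sinus, than about a strip with nine seconds of AF, which must be.

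These strips enter the SR column of Table 7. An Irregular call on one becomes n11, an error on sinus rhythm. A Not AF call becomes n21, a correct sinus negative. The strips are also absent from every output conditioned on Other Irregular Rhythm, and a notification whose strips hold only short AF counts as neither AF nor other in the combined PPV. Subjects with intermittent AF are the likeliest source, because strips can straddle an onset or offset; they are the target of Cohort 3 (54 to 394 subjects in the synopsis).

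**Working it through.** **Routing.** The four steps applied to a strip with AF under 10 seconds:

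| Strip also contains | Fewer than 6 uninterpretable sub-strips | 6 or more |
|---|---|---|
| nothing else | Sinus rhythm | Unreadable |
| SVT, VT, heart block or sinus arrhythmia | Other | Unreadable |
| PACs or PVCs | Other (AF if the second sentence of step 1 is read alone) | Unreadable (AF on the same reading) |

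Only the first cell of the first row is at fault.

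**Which metrics depend on the label.** Moving these strips from Sinus rhythm to Other shifts Irregular calls from n11 to n14 and Not AF calls from n21 to n24.

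- FPR uses n11+n14 over nSR+nOA: both sums are unchanged.
- PPV uses n12, n13, nTI and n15: all unchanged.
- AFBF specificity uses n21+n23+n24 over nSR+nAFL+nOA: unchanged.
- IRNF specificity, n21/nSR, changes.
- NPV, n21/(nTN−n25), changes, because n24 stays in the denominator but leaves the numerator.

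**Size.** The plan states no figure to reproduce. Let f be the share of sinus-labelled strips that hold short AF, q the Irregular rate on them and s the Irregular rate on true sinus strips. Then

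loss in specificity = f × (q − s).

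The documents give none of these. The illustration below assumes 10,000 sinus-labelled strips with s = 0.5%, 2,000 AF strips at 95% sensitivity and 1,500 Other strips with 5% Irregular.

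Worked case, f = 0.5% and q = 50%: 50 short-AF strips, 25 called Irregular.

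- As written: n11 = 9,950 × 0.005 + 25 = 74.75 and n21 = 9,925.25. Specificity = 9,925.25/10,000 = 99.25%.
- After relabelling: n21 = 9,900.25 and nSR = 9,950. Specificity = 99.50%.
- FPR: (74.75 + 75)/11,500 = 1.30% as written and (49.75 + 100)/11,500 = 1.30% after.
- NPV: nTN = 9,925.25 + 100 + 1,425 = 11,450.25 in both cases. NPV = 86.68% as written and 9,900.25/11,450.25 = 86.46% after.
- Pr(Irregular given Other): 75/1,500 = 5.00% as written and 100/1,550 = 6.45% after.

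| f | q | Specificity: written → relabelled | NPV: written → relabelled | FPR (both) | Irregular given Other: written → relabelled |
|---|---|---|---|---|---|
| 0.1% | 10% | 99.49% → 99.50% | 86.71% → 86.63% | 1.10% | 5.00% → 76/1,510 = 5.03% |
| 0.5% | 50% | 99.25% → 99.50% | 86.68% → 86.46% | 1.30% | 5.00% → 6.45% |
| 2% | 10% | 99.31% → 99.50% | 86.69% → 85.12% | 1.25% | 5.00% → 95/1,700 = 5.59% |
| 2% | 90% | 97.71% → 99.50% | 86.50% → 86.32% | 2.64% | 5.00% → 255/1,700 = 15.00% |

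**A rough guide to f.** Assume 60-second strips (the length is not stated) and episode boundaries falling at random within them. The share of one subject's strips that straddle a boundary and hold under 10 seconds of AF is episodes × 2 × 60/(13 × 86,400) × 10/60. For 100 episodes this is 1.07% × 1/6 = 0.18%; for 50 and 200 it is 0.09% and 0.36%. With f = 0.18%, q = 50% and s = 0.5%, the loss is 0.0018 × 0.495, about 0.09 percentage points in that subject. With 50 episodes and q = 10% it is 0.0009 × 0.095, under 0.01 points. Two cautions apply. The 0.18% is a share of all strips, so f among sinus-labelled strips is larger when the subject spends much time in AF. Isolated runs under 10 seconds are not counted.

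**The case against.** The strongest reply is that the 10-second minimum is intended. It appears in step 1 and again in the notification-level PPV of Section 6.2.3. Under that definition the strip is not strip-level AF, so an Irregular call counts against the device whether the label is Sinus rhythm or Other. This stands. A reader might infer that the sequence itself turns correct detections of AF into device errors, or that it biases FPR, PPV or the Cohort 2 comparison. The formulas do not support that.

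Three further inferences also fail. First, not every short-AF strip is affected: a PAC, PVC or sinus arrhythmia elsewhere in the strip sends it to Other. Second, a share of strips near 0.18% is not comparable with a false-call rate of similar size. It would have to be multiplied by q − s, and q near 100% is unlikely for a strip that is more than five-sixths non-AF under the 60-second assumption. Third, one might say that these seconds count as AF in the AFBF burden reference but as sinus in the strip reference. That depends on the minimum episode length in the patch read, which is not visible in Section 5.5.2.1. AFBF specificity pools sinus and other rhythms anyway.

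It can also be said that relabelling lowers NPV and puts AF into a category defined as non-AF. Both are true. A separate sub-category and reporting with and without it deal with the second; the first is a cost. The threshold explains why the strip is not called AF. It does not explain why it is called sinus.

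**Conclusion.** The point holds for readable strips with AF under 10 seconds and no other listed arrhythmia. The visible, unredacted steps give them a wrong label. The outputs affected are IRNF tachogram specificity and NPV, the Section 6.2.5 results for Other Irregular Rhythm, and the combined AF-or-other notification PPV. The bias in specificity is downward only if short AF triggers Irregular calls more often than sinus rhythm does.

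The IRNF primary endpoint is unaffected because it uses patch AF of at least 30 seconds, and the AFBF primary endpoint because it uses patch burden. The Cohort 2 FPR test is unaffected provided it uses the Section 6.2.3 formula; part of its hypothesis text is blacked out.

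The true size cannot be computed, since strip length, the frequency of short AF and the call rates are not given. It is probably small. Across the assumed grid the loss in specificity runs from 0.01 to 1.79 percentage points, with the top of that range needing 2% of sinus-labelled strips to hold short AF and 90% of those to be called Irregular. It is worth correcting because it is cheap now, whereas a strip already labelled Sinus rhythm carries no mark of short AF and could be recovered only by re-reading.

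**What to change.** Before adjudication starts:

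- In step 3, after the non-AF arrhythmia condition, add *or any atrial fibrillation lasting less than 10 seconds*. Code such strips as Other with the sub-category *AF under 10 s*, so that they appear in the Section 6.2.5 sub-category tables.
- State that the 10-second minimum also governs the step 1 sentence on AF with PACs or PVCs. Reading that sentence alone would move strips to AF, and that move, unlike the one above, would change FPR and PPV.
- Report the conditional probabilities for Other Irregular Rhythm with and without the new sub-category.
- Say that the sub-category counts as positive in the combined AF-or-other notification PPV. The person-level analyses listed beside it require at least 10 seconds, so the difference should be stated.

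The cost is one clause, one code and no extra reads. Stated NPV falls slightly because its formula credits only n21: by 0.08 to 1.57 percentage points in the four illustrated cases, the largest at f = 2% and q = 10%. FPR, PPV and AFBF specificity stay as they are; this change is not meant to move them.
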